**SYSTEMATIC INVESTIGATION OF BLACKS WITH STROKE- GENOMICS
(SIBS-GENOMICS) STUDY**

SEPTEMBER 5TH, 2022

PILOT TRIAL

Specific Aim. To determine the effectiveness of the Afrocentric stroke riskometer mobile phone application combined with the motivation stroke educational video and educational modules for improvement of individual awareness and reduction of the total quantitative risk of stroke through a randomized controlled trial among stroke-free adults in Nigeria and Ghana.

Study design: A feasibility pilot study involving stroke-free adults with at least 2 vascular risk factors for stroke assigned to an educational intervention for 2 months comprising of a stroke video and riskometer App aimed at improving stroke risk factor awareness and health seeking behavioural modification to control vascular risk (n=50) compared with a control group (n=50) who are offered one time counselling.

Study Sites: 3 sites across Nigeria and Ghana

Study Participants: Study participants will be CONSECUTIVELY selected from the existing pool of stroke-free controls in SIREN and SIBS Genomics studies across the 3 study sites (60 from Ibadan, 20 from Kumasi and 20 from Zaria). The vascular risk factor profile of these control participants has already been assessed. Stroke free status at enrollment will be reconfirmed using the locally validated version of the QVSFS.

Eligibility criteria: **Inclusion criteria:** (i) male or female (sex is a biologic variable of interest), (ii) age \geq 18 years, (iii) with at least 2 stroke risk factors based on the list of 11 topmost modifiable risk factors identified in the SIREN study (including hypertension, diabetes mellitus, dyslipidemia, smoking, overweight, physical inactivity, or unbalanced/poor diet). (iv) ownership or access to smartphone in consenting stroke-free adults. **Exclusion criteria:** prior history of vascular disease (e.g., stroke, transient ischemic attack, angina, myocardial infarction, peripheral vascular disease, and atrial fibrillation), or cognitive impairment; not comfortable reading and writing, depression or other psychiatric disorders (through personal declaration) likely to affect the interventions; participation in another RCT; other conditions rendering the individual unsuitable to participate in this research as judged by treating physicians,

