Statistical Analysis: For this pilot trial, our sample size focused on precision of estimates for a future study design rather than power of statistical tests. We will compare medians and means for continuous variables using either the Mann-Whitney's U-test or Student's t-test (paired) while categorical variables will be compared using the Chi-squared tests. A $p < 0.05$ was considered significant difference between the 2 groups. Unadjusted odds ratios were calculated for primary outcome measures.

Qualitative Interviews: We will conduct key informant interviews (KIs) with intervention participants to explore personal perspectives on acceptability of the app and video, including barriers and facilitators of its use, behavioral change efforts made to reduce stroke risk, and recommendations for revision and educational module content. Educational module content via a wireframe of app content will be shared with participants to ascertain their perceptions and recommendations for content refinement. Additionally, factors related to the social determinants of health (SDOH) will be included to better understand influence on lifestyle modification, stroke risk, and access to care and adoption of recommended health behaviors. Clinician KIs will be completed to explore their acceptance and readiness to use the app, input of current treatment practices, recommendations for educational module content, behavioral modification strategies, clinical team educational needs, and barriers and facilitators toward intervention implementation. Interviews will be audio-recorded, transcribed and translated to English when necessary, and thematically analyzed using inductive and deductive approaches.

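### The pilot is sized for precision of estimates, but its analysis judges between-group differences by p<0.05, a verdict unreliable in both directions at 50 per arm

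*Protocol*

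**What the plan says.** All references are to the Protocol; no SAP is at hand.

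- **Sample size.** The Study design section sets 50 per arm, and Study Participants splits the total by site: "60 from Ibadan, 20 from Kumasi and 20 from Zaria".
- **Basis of the sample size.** Statistical Analysis: "our sample size focused on precision of estimates for a future study design rather than power of statistical tests". No target interval width, SD, event rate, effect size or dropout is given.
- **Decision rule.** The same paragraph compares continuous measures "using either the Mann-Whitney's U-test or Student's t-test (paired") and categorical measures by chi-squared, then states that p<0.05 "was considered significant difference between the 2 groups".
- **Effect measure.** The paragraph closes with: "Unadjusted odds ratios were calculated for primary outcome measures". Outcome measures has three groups (feasibility, satisfaction and acceptability, signal of efficacy) and labels nothing in them as primary.
- **Aim.** Specific Aim: "To determine the effectiveness of the Afrocentric stroke riskometer mobile phone application", combined with the video and modules. Study design calls the same trial a feasibility pilot.

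**The concern.** One paragraph sets aside the power of tests as a basis for the design and then makes a test the criterion for a difference. A significance rule applied to many outcomes, with no primary outcome and no multiplicity rule stated, gives a substantial chance of a spurious positive. At 50 per arm it also gives a large chance of calling a real, modest effect non-significant.

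The pilot's stated purpose is to inform a future study. That study will need the SD of the risk-score change, the completion and doctor-visit proportions, and the size of the between-arm differences, each with its uncertainty. A significant or not-significant label supplies none of these. Set under an aim of determining effectiveness, it could be read as a reason to go ahead or to stop.

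**Working it through.** **The plan's own figure.** The total can be checked only for consistency: 50 + 50 = 100 and 60 + 20 + 20 = 100. It cannot be reproduced from a precision target, because none is given.

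**How many measures can be compared between arms (Outcome measures section).**

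- Feasibility lists 6. Four of them (approached, refused, ineligible, enrolled) arise before randomization and cannot differ by arm, which leaves 2: completion and doctor visits.
- Satisfaction and acceptability lists 5. The fifth, adherence, names five components (medication, physical activity, diet, alcohol, cigarettes). Analysed separately, they bring the group to 9.
- Signal of efficacy lists 3: change in risk score, change in awareness score, provider encounters.

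As listed: 2 + 5 + 3 = 10. With adherence split: 2 + 9 + 3 = 14.

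**Chance of at least one p<0.05 when nothing differs.** Sidedness is not stated; two-sided is assumed. For independent tests the formula is 1 − 0.95^k. For correlated tests, equicorrelated normal test statistics are used.

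| Tests k | Independent | Correlation 0.3 | Correlation 0.5 | Expected false positives (0.05 × k) |
|---|---|---|---|---|
| 10 | 1 − 0.95^10 = 40% | 35% | 29% | 0.5 |
| 14 | 1 − 0.95^14 = 51% | 44% | 35% | 0.7 |

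**Chance of detecting a real effect on one measure.** Two-sample t-test, 50 per arm, two-sided 0.05. The effect sizes are assumptions, since the Protocol gives none.

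| True effect | Power |
|---|---|
| 0.2 SD | 17% |
| 0.3 SD | 32% |
| 0.5 SD | 70% |
| 0.57 SD | 80% |

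At 0.3 SD the rule misses the effect in 100 − 32 = 68% of pilots.

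**What a significant result would look like.** The critical difference is t(0.975; 98) × √(2/50) = 1.984 × 0.2 = 0.40 SD. If the true effect is 0.3 SD, every significant result in the right direction comes from an observed difference of at least 0.40 SD. A later trial designed on significant results alone would start from an overestimate.

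**What 50 per arm does deliver, as 95% confidence interval half-widths.**

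- Mean difference: the same 1.984 × √(2/50) = ±0.40 SD.
- One arm's proportion at 50%: 1.96 × √(0.25/50) = ±14 points.
- Difference in proportions at 50%: 1.96 × √(2 × 0.25/50) = ±20 points.
- Pooled SD on 98 degrees of freedom: factors √(98/χ²) of 0.88 to 1.16, so about −12% to +16%.

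These are the quantities that the sample-size sentence appeals to, and the section states none of them.

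**The case against.** The strongest defence is that the Protocol is open about the lack of power. It calls the trial a feasibility pilot, labels the clinical outcomes as signals, and ties no progression decision to p<0.05. Interval estimates, effect scales and multiplicity rules are ordinary SAP content. This part stands: the absence of confidence intervals would not by itself be a finding. What does not go away is that the Protocol itself fixes the significance criterion, beside a sentence that disclaims power and under an aim of effectiveness.

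A reader might infer more than the text supports:

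- **That a chance finding is probable.** It passes one half only with 14 independent tests. On the 10 listed measures it is at most 40%, and outcomes such as doctor visits and encounters are plausibly correlated.
- **That at least 14 tests are planned.** The Protocol does not say that adherence will be split. Even 10 may be high: the statement that measures will be compared between groups sits in the feasibility item, the satisfaction questionnaire may apply to one arm only, and the knowledge and awareness measures may overlap.
- **That the pilot will yield no design inputs.** Arm-level means, medians and proportions would still be produced. What the section lacks is a stated precision for them, and an SAP could add it.
- **That the odds ratio must go.** It is tied to unnamed primary outcomes, not expressly to score changes or counts, and it is a legitimate scale for binary outcomes. Nor does high completion often make it undefined. At an assumed 97% completion in both arms, at least one arm has no non-completers in 1 − (1 − 0.97^50)² = 39% of pilots, but the ratio is truly undefined (0/0) only when both do, (0.97^50)² = 4.8%. In the other 34% it is 0 or infinity, which exact or continuity-corrected methods handle.

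**Conclusion.** The concern holds as a conflict between the stated basis of the sample size and the stated decision rule. With no effect, roughly three to five pilots in ten would show at least one p<0.05: 29–40% over 10 measures, 35–51% over 14. With a true 0.3 SD effect, about two in three would miss it on a given measure. The verdict is therefore unreliable in both directions and does not inform the next study.

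The ranges rest on assumptions: two-sided tests, 10 to 14 comparable measures, a common correlation from 0 to 0.5, the effect sizes shown, and no loss to follow-up. Losses would lower the power. The conflict itself needs none of these; it lies in the wording. The change should be made, since the trial can still be run and analysed but its conclusions are open to misreading.

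**What to change.** In Statistical Analysis, replace the p<0.05 sentence with text such as:

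> For each measure, arm-specific estimates and the between-arm difference will be reported with 95% confidence intervals, including the SD of the risk-score change and the completion and doctor-visit proportions. Any p-values are exploratory, and no conclusion on effectiveness will be drawn from them. With 50 per arm, the expected half-width is about ±0.40 SD for a mean difference and, at a proportion of 50%, ±14 points for one arm and ±20 points for a difference.

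Report the four pre-randomization proportions overall, not by arm. Keep the odds ratio for binary outcomes if wanted, with its interval and beside the risk difference, and say which outcomes it applies to. Use a mean difference for score changes and a rate ratio or rate difference for encounter counts. Reword the Specific Aim to assessing feasibility and estimating the signal of effect with its uncertainty.

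The cost is wording only, with no extra data or participants. The one thing given up is a significance headline.
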